3.1 Description

The zipper wound technology is a new wound closure device that is an alternative to the commonly used conventional staples and sutures. The device acts like a scaffold to stabilize the adjacent sides of a wound in order to minimize forces that can disrupt normal healing of the skin. The other treatment groups include monocryl + Dermabond (conventional sutures and skin adhesive glue) and polyester mesh + Dermabond. All products have been FDA approved.

3.2 Method for Assigning Subjects to Treatment Groups

Names of patients who are consented for the study will be inputted into a computer and randomized to one of the three treatment groups based on an alternating method. A randomized control trial will provide the highest level of evidence without altering the potential risks to the patient as all three wound closure techniques have been found to have comparable complication rates.

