2.6 Subject Recruitment and Screening

All participants will be initially identified by participating surgeons among a large patient population scheduled for joint arthroplasty.

This study will be discussed with eligible patients by their surgeon at one of their pre-operative clinic visits. Research assistants working for the orthopaedics department will meet with patients during their pre-op visit to explain the study and obtain written informed consent using the IRB-approved consent form. A study log of consented patients will be maintained in a de-identified manner.

3 Study Treatment

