3.4 Blinding of Study Product

Given the nature of the application of the wound closure device, which will be visible to the surgeon at the time of application and the patient postoperatively, the study will not be blinded to either the surgeon or the patient. Prior to discharge, a blinded plastic surgeon will be asked to assess the wound based on comessis and overall quality of wound healing.

4 Study Procedures

Patients who are eligible for the study will be notified on a preoperative visit via a tool on the electronic medical record system (Epic).

At this time, surgeon research assistant will ask the patient if they would like to be involved in the study. If consent to participate in the study is given, the surgeon will go ahead with the randomization process, which will dictate what type of wound closure device will be used at the time of the surgery. All of the wound devices are currently being used at the institution. The study will follow normal standard of care for the application of these devices. The only different will be the randomization process that will take place prior to the surgery. Data will be collected regarding the primary outcomes at the time of discharge as well as at their normally scheduled postoperative visits. Patients will be followed up to their 3rd postoperative visit. Prior to discharge, a plastic surgeon, who will be blinded to the type of wound closure technique that the patient received, will assess the wound for the quality of wound healing. At their postoperative visits, the physician will document whether a complication had occurred. Patients will also be given patient-reported outcome questionnaires, including VAS scores and HWES, that will measure the level of satisfaction of their wound healing at the time of these visits.

The following table shows the visits and procedures/ observational data collection that will occur during the study:

Activity	Pre-operative assessment	Date of surgery	Prior to discharge	Postop visit #1	Postop visit #2	Postop visit #3
Study team procedures						
Consent	X					
Medical History	X			X	X	X
Physical Exam	X		X	X	X	X
Height	X			X	X	X
Weight	X			X	X	X
Vitals signs	X		X	X	X	X
Record of			X	X	X	X

CONFIDENTIAL

This material is the property of the NYU School of Medicine and Langone Medical Center. Do not disclose or use except as authorized in writing by the study sponsor

complications						

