Perioperative costs – cost of supplies, time to wound closure, operative times, length of stay, readmissions		X	X			
Randomization		X				
Study treatment dispensation		X				
Subject Survey – VAS score, HWES score			X	X	X	X

5 Statistical Plan

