5.2 Statistical Methods

Data on patient baseline characteristics, procedural characteristics, perioperative outcomes, functional outcomes, and costs will be collected. Single variable and multivariate statistical analysis will be performed to assess the aforementioned data points. Dichotomous data outcomes will be analyzed using odd ratios and chi-squared tests while continuous data points will be analyzed using Student t-tests. Each complication will be documented for every patient. The rates of complication will be analyzed individually for each technique, and risk ratios will be conducted between techniques to determine which technique has the lowest risk of developing a complication. Complications include infection, abscess formation, dehiscence, prolonged drainage, allergic reactions, among others. Cost effectiveness will be determined by the differences in quality metrics such as LOS, readmissions, cost of supplies, and differences in wound closure time between the different wound closure techniques. Each of these variables will be calculated based on the associated hospital costs and analyzed to determine the most cost effective wound closure technique.

CONFIDENTIAL

This material is the property of the NYU School of Medicine and Langone Medical Center. Do not disclose or use except as authorized in writing by the study sponsor

6 Safety and Adverse Events

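### Section 3.2 allocates patients by an alternating method with no stated concealment, and Section 4 has the surgeon proceed with it, so the text does not support the claim that the trial is randomized

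*Combined protocol and SAP*

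**What the plan says.** - **Method.** Section 3.2 says the names of consented patients are "inputted into a computer and randomized to one of the three treatment groups based on an alternating method". The same section relies on the design for its strength: "A randomized control trial will provide the highest level of evidence".
- **Who finds the patients.** Section 2.6: "All participants will be initially identified by participating surgeons among a large patient population". Surgeons also raise the study with eligible patients. Research assistants obtain the written consent.
- **Who allocates.** Section 4: once consent is given, "the surgeon will go ahead with the randomization process, which will dictate what type of wound closure device will be used".
- **Blinding.** Section 3.4: "the study will not be blinded to either the surgeon or the patient". The one blinded role is a plastic surgeon who rates the wound before discharge.
- **When.** Section 4 ties the step to consent and then says "The only different will be the randomization process that will take place prior to the surgery". The schedule table in Section 4 marks "Randomization" under the date of surgery.
- **Analysis.** Section 5.2: "Single variable and multivariate statistical analysis will be performed to assess the aforementioned data points". No covariates are named.

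The documents mention no block scheme, seed, sealed envelopes, central service or independent custodian of a list.

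**The concern.** Alternation and randomization are different things, and Section 3.2 uses both words in one sentence. A rotation through three arms is deterministic, and running it on a computer does not make it random. Anyone who can see the last assignment knows the next one before a patient is approached.

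There is room to act on that knowledge. Section 5.1 expects only half of about 700 patients to be approached and gives no rule for which half. Section 1.1 states a hypothesis in favour of the zipper. Obtaining consent before allocation does not protect, because under a rotation the arm due is known before consent is sought.

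Nothing later in the plan repairs selection at entry. The plastic surgeon's rating comes after it. Complications, the primary endpoint, are documented by the treating physician with no blinding stated. A multivariable model can adjust only for what was measured.

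**Working it through.** The plan gives no figure for this point, so there is none to reproduce. The check has three parts.

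**1. The text.** Sections 2.6, 3.2, 3.4, 4 and 5 were read together. Section 3.2 is the only description of how the sequence is made, and the rule it names is alternation. The timing statements can be reconciled (consent at the preoperative visit, allocation on the day of surgery), but the Section 4 wording can equally mean allocation straight after consent. One time should be stated.

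**2. How predictable the next arm is.**

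- Rotation, last assignment visible (assumption): certain after the first patient. Concealed random list: 1/3, or 33%.
- Rotation, each of K surgeons seeing only their own patients (assumed equal, random caseload). Guessing the next arm in the cycle is right when the surgeon's next patient is 1, 4, 7, … places after their last, so the probability is (1/K) / [1 − (1 − 1/K)³]:

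| K | Probability correct |
|---|---|
| 1 | 1.00 |
| 2 | 0.50 / 0.875 = 0.57 |
| 5 | 0.20 / 0.488 = 0.41 |
| 10 | 0.10 / 0.271 = 0.37 |

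- Permuted blocks of 3, 6 or 9 with past assignments visible, guessing the arm with the fewest patients so far: about 55% (simulation, 2,000 lists of 201). Concealment therefore matters more than the type of list.

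**3. What steering could do to the result.** The documents give no complication rates or risk strata, so every input here is assumed except the arm size: 200/3, about 67, from Section 5.1. The share of patients at high risk is h = 0.30, with complication rates of 20% (high risk) and 5% (others) and no true device difference. A fraction q of high-risk candidates is passed over when the zipper is due, and the other arms are unaffected.

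- High-risk share in the zipper arm: h(1 − q)/(1 − hq).
- Rate in the other arms: 0.30 × 0.20 + 0.70 × 0.05 = 0.095.
- q = 0.5: share 0.15/0.85 = 0.176; zipper rate 0.176 × 0.20 + 0.824 × 0.05 = 0.0765; risk ratio 0.0765/0.095 = 0.80.
- q = 1: share 0; zipper rate 0.05; risk ratio 0.05/0.095 = 0.53.

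False-positive rates at the 5% level, by exact binomial enumeration:

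| Test | q = 0 | q = 0.5 | q = 1 |
|---|---|---|---|
| 67 vs 134, uncorrected chi-squared | 4.8% | 6.1% | 17.4% |
| 67 vs 134, continuity-corrected | 2.6% | 3.1% | 10.0% |
| 67 vs 134, Fisher | 3.5% | 4.4% | 13.6% |
| 67 vs 67, uncorrected chi-squared | 5.1% | 6.8% | 17.0% |

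Range over the inputs (67 vs 134, uncorrected chi-squared):

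| Inputs | q | Risk ratio | False positives |
|---|---|---|---|
| h = 0.20, 10% vs 5% | 0.5 | 0.93 | 4.3% |
| h = 0.20, 10% vs 5% | 1 | 0.83 | 4.6% |
| h = 0.40, 30% vs 5% | 0.5 | 0.75 | 10.2% |
| h = 0.40, 30% vs 5% | 1 | 0.33 | 58.4% |

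**The case against.** The fairest defence is that the wording is loose. Section 3.2 mentions a computer and the word randomized, so alternating may be a careless description of a balanced random list, and unstated concealment may exist. The surgeon may do no more than trigger a computer step. The surgeon's lack of blinding, as Section 3.4 explains it, concerns seeing the device at application, not foreseeing the arm. Section 8.1 also provides for biweekly review of recruitment and protocol adherence.

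Much of this is fair, and it limits the conclusion to what the text supports: it cannot be said that allocation was predictable in practice. But triggering a computer step does not help if the computer rotates, and reviewing recruitment is not concealment.

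The illustration can also be challenged. It pools the two comparators, whereas the plan compares techniques with each other. At 67 vs 67 the most extreme corner falls from 58.4% to 50.5%. It also models removal only. If the passed-over high-risk patients enter the other arms instead, so that the overall mix stays at 30%, half steering gives a risk ratio of 0.73 and 8.2% false positives. These points change the size of the illustration, not the defect.

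Finally, the timing statements can be read as compatible, and permuted blocks are only one acceptable kind of list. Both points stand, and both are secondary.

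**Conclusion.** The concern holds. As written, the only stated allocation rule is a predictable rotation. It contradicts the word randomized in its own sentence, and no concealment is described. This is a wrong stated rule and not merely a missing detail. It must be fixed, because selection at entry cannot be undone after enrolment and the study's main claim to strength depends on random allocation.

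The size of any bias is unknown. On the assumed inputs, half steering by removal moves a true risk ratio of 1 to between 0.93 and 0.75, and full steering to between 0.83 and 0.33. Under partial steering by removal the main harm is a biased estimate; in the base case the false-positive rate rises only from 4.8% to 6.1%. These figures require that past assignments are visible and that someone acts on them. The documents establish neither.

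**What to change.** In Section 3.2, replace the reference to alternation with text such as:

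> Patients will be assigned 1:1:1 by a computer-generated random list (permuted blocks of varying, undisclosed size). The list will be prepared and held by staff who neither recruit nor operate, and concealed in a password-protected module or sealed opaque envelopes. Each assignment will be released only after consent and enrolment are recorded.

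Concealment and independent custody are the essential part; another form of random list would also serve.

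In Section 4, state that the surgeon does not run the allocation, and give one time of allocation that agrees with the schedule table.

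If a proper concealed list is already in use, describe it. If patients were in fact assigned by alternation, call the trial quasi-randomized throughout and remove the claim in Section 3.2 about level of evidence.

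The cost is a short amendment, which goes to the IRB, and naming a custodian for the list. The documents do not identify that person, and the research assistants who obtain consent should not fill the role. A computer is already used for allocation. No extra patients or visits are needed.

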3.3 Preparation and Administration of Study Product

The three different treatment devices will be administered following the normal standard of care. All three wound closure devices are currently being used at NYULMC. No modifications to the normal standard of practice other than the randomization process will be implemented.

CONFIDENTIAL

This material is the property of the NYU School of Medicine and Langone Medical Center. Do not disclose or use except as authorized in writing by the study sponsor

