A single-center, phase IV, randomized, prospective study investigating the efficacy of various wound closure devices in reducing postoperative wound complications

Regulatory Sponsor: **[name]**

Co-Investigators: [name]
[name]

NYULMC Orthopaedic Surgery
Hospital of Joint Diseases
[name]
[name]

Study Product: Zipper wound closure device, Monocryl + Dermabond,
Polyester mesh + Dermabond

Protocol Number: s16-02020

NCT Number: NCT03134209

Version: 1/10/17

CONFIDENTIAL

This material is the property of the NYU School of Medicine and Langone Medical Center. Do not disclose or use except as authorized in writing by the study sponsor

Initial version: 12/15/16

List of Abbreviations

TJA- Total joint arthroplasty

CONFIDENTIAL

This material is the property of the NYU School of Medicine and Langone Medical Center. Do not disclose or use except as
authorized in writing by the study sponsor

Study Summary

Title	A single-center, phase IV, randomized, prospective study investigating the efficacy of various wound closure devices in reducing postoperative wound complications
Short Title	Assessing various wound closure techniques; RCT
Protocol Number	i16-02020
Phase	4
Methodology	Randomized, control
Study Duration	7 months
Study Center(s)	Single-center
Objectives	To determine the efficacy of the experimental wound closure device in regards to reducing wound complications and costs
Number of Subjects	200 subjects
Diagnosis and Main Inclusion Criteria	Patients who are undergoing joint arthroplasty
Study Product, Dose, Route, Regimen	Zipper surgical skin closure device applied to the most superficial layer of skin following a joint arthroplasty
Duration of administration	Applied one-time to close the wound following joint arthroplasty. This device will be applied for up to 2-3 weeks
Reference therapy	Experimental treatment will be compared to two groups: 1) Monocryl + Dermabond 2) Polyester mesh + Dermabond
Statistical Methodology	Odd ratios will be used to determine which wound closure device is at higher risk of developing a wound complication

CONFIDENTIAL

This material is the property of the NYU School of Medicine and Langone Medical Center. Do not disclose or use except as authorized in writing by the study sponsor

Introduction

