1.1 Background

Today's healthcare climate continues to emphasize the need for high-quality of care while minimizing the financial burdens of the patient, hospital, and payer. This is particularly relevant in total joint arthroplasty (TJA) as payment models are shifting toward bundled, pay-for-performance episodes of care,[1, 2] and away from the current plan of payments for each separate service provided. Given that the demands for TJA are projected to increase substantially for decades to come,[3] it is imperative to identify potential factors that may improve clinical outcomes, so that ultimately, costs per episodes of care are minimized.

One such area of improvement involves gaining a better understanding of the optimal wound closure technique following TJA. Specifically, two measures, wound closure times and surgical outcomes, have been the focus of prior studies as they have been closely associated with avoidable healthcare expenditures. Common complications of failed wound closures include infection, dehiscence, edema, and arthrofibrosis.[4-15] Not only do these failures lead to exorbitant costs through poorer outcomes (i.e. delayed progress in physical therapy, increased length of stay, increased readmission, and reduced patient satisfaction), they are also known to have a significant impact on the overall long-term health of the patient.

The three common options for wound closure following TJA include sutures, staples, and skin adhesives. While conventional sutures and staples have been the mainstay techniques in TJA for some time, the barbed suture is a newer technique that has emerged as a popular option within the last decade. Reported advantages of this technique include the need for less material per incision, lower closure costs, shorter length of closure time, and a knotless application of the suture. [8-11, 16] Outcomes in regards to complications have been variable when compared to conventional sutures in TJA.[8-11] The skin adhesive that is most commonly used today includes a 2-octyl cyanoacrylate (OCA), high-viscosity, flexible glue.[7, 17] This technique has been associated with decreased wound closure times,[18] high satisfactory cosmetic results,[17, 19] and surgical outcomes comparable to conventional sutures.[17, 20] Other newer techniques such as the zipper technique[21] and variations of the OCA skin adhesives have also been sources of experimentation.

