2.3 Secondary Study Endpoints

Cost effectiveness will be determined by the increased LOS, readmissions, cost of supplies, and differences in wound closure time between the differences in wound closure techniques. Each of these variables will be calculated based on the associated hospital costs and analyzed to determine the most cost effective wound closure technique.

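### Surgeon is neither an allocation stratum nor a named covariate, and wound closure time has no start or stop point, so the device comparison loses precision

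*Combined protocol and SAP*

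**What the plan says.** All references are to the combined protocol and SAP.

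- **What the device closes.** The Study Summary describes the experimental product as "Zipper surgical skin closure device applied to the most superficial layer of skin following a joint arthroplasty". Skin-only use is explicit for the zipper. For the two comparators it is a reasonable inference, not a statement.
- **Everything else.** Section 3.3 says "No modifications to the normal standard of practice other than the randomization process will be implemented". Closure of the layers beneath the skin is not described anywhere, and it is not a listed data item.
- **Surgeons.** Section 2.6 says "All participants will be initially identified by participating surgeons", so there is more than one. Their number and caseloads are not given.
- **Allocation.** Under Section 3.2 patients are "randomized to one of the three treatment groups based on an alternating method". No stratification is named. Section 4 adds that after consent "the surgeon will go ahead with the randomization process", before the operation. Section 3.4 states that the surgeon is not blinded.
- **Closure time.** Section 2.3 bases cost effectiveness in part on "differences in wound closure time between the differences in wound closure techniques". The schedule in Section 4 lists time to wound closure and, separately, operative times. Neither place says when the closure clock starts or stops. The cost objective in Section 1.4 uses total length of operation.
- **Analysis.** Section 5.2 names odds ratios and chi-squared tests for dichotomous outcomes and Student t-tests for continuous ones. It also mentions a multivariate analysis and the collection of procedural characteristics, without naming a model or any covariate.

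**The concern.** The arms differ in the skin step. If the clock covers the whole wound, the recorded time adds deep-layer work that the assigned device does not do, together with its variation between patients and surgeons. A surgeon's habits can also affect operating time, length of stay and complications, and nothing in the allocation or the named tests removes that variation.

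The time measure carries weight. Section 10.2 states that the three techniques do not differ in supply cost, so the cost reduction hypothesised at the end of Section 1.1 has to come from time, length of stay, readmissions and complications. An undefined and noisy closure time weakens that conclusion. It also cannot easily be repaired later, because a time stamp not taken in theatre may not be recoverable.

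There is also a route to bias. The surgeon knows the arm before operating and could close the deeper layers differently according to the device to come.

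**Working it through.** The plan gives no figure for closure time, its SD, or variation between surgeons, so there is no stated value to reproduce. The inputs marked as assumptions below are illustrations.

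**Arm size.** 200 patients at 1:1:1 (Section 5.1): 200/3 = 66.7, taken as 67.

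**1. Whole-wound timing against skin-step timing.** Assumptions: SD of the skin step 2 min; SD of the deep layers 2 to 4 min; the two independent. SE of a difference between two arms = SD × sqrt(2/67) = SD × 0.173. Detectable difference = (1.96 + 0.84) × SE = 2.80 × SE (two-sided 0.05, 80% power, no multiplicity adjustment).

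| What is timed | SD (min) | SE (min) | Detectable difference (min) |
|---|---|---|---|
| Skin step only | 2 | 0.35 | 0.97 |
| Whole wound, deep SD 2 | sqrt(4 + 4) = 2.83 | 0.49 | 1.37 |
| Whole wound, deep SD 4 | sqrt(4 + 16) = 4.47 | 0.77 | 2.16 |

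The variance rises 8/4 = 2 to 20/4 = 5 times.

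**2. Adjusting for surgeon.** Assumption: surgeon explains a share r of closure-time variance. Reduction in SE = 1 - sqrt(1 - r), ignoring the few degrees of freedom spent.

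- r = 0.20: 1 - sqrt(0.80) = 11%. An unadjusted test needs 1/0.80 = 1.25 times the patients.
- r = 0.50: 1 - sqrt(0.50) = 29%. An unadjusted test needs 1/0.50 = 2 times the patients.

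**3. Chance imbalance by surgeon.** Assumption: one surgeon does 40% of cases (80 of 200), split at random. The probability that two arms of 67 differ by 10 points or more in that surgeon's share is about 25%. This assumes a random split, which is not the alternating mechanism that Section 3.2 describes.

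**4. Complications (primary endpoint).** Suppose a background technique or surgeon accounts for a fraction q of cases and changes complication risk by 5 to 10 points (assumptions). The 95% limits for chance imbalance are 1.96 × sqrt(2q(1 - q)/67).

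- q = 0.10: ±10 points, a shift in the arm comparison of 0.5 to 1.0 points.
- q = 0.50: ±17 points, a shift of about 0.9 to 1.7 points.

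For scale, at an assumed 10% complication rate the SE of a difference is sqrt(2 × 0.10 × 0.90/67) = 5.2 points. The effect on the primary endpoint is therefore small beside its sampling error.

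**5. If technique did depend on arm.** With use differing by 10 to 40 points between arms and the same 5 to 10 point risk difference, the bias is 0.10 × 0.05 = 0.5 points up to 0.40 × 0.10 = 4 points. Nothing in the documents says that use differs by arm.

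**The case against.** The strongest reply is that this is a pragmatic comparison. Usual practice outside the assigned device is a legitimate choice, and under sound randomization its variation is balanced on average and already reflected in the standard error. That stands. It does not excuse leaving an endpoint undefined or setting aside a known source of variation.

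A reader might infer that surgeon is wholly unaccounted for. The documents do not support that. Section 5.2 plans to collect procedural characteristics and to run a multivariate analysis, and surgeon could enter there. The wording commits to nothing, but it is not an exclusion. Nor do the documents rule out alternation run separately by each surgeon, which would come close to balance within surgeon; they do not say at what level it runs.

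A reader might also take Section 1.1 as evidence that deep-layer suture choice drives these endpoints, since it says of barbed suture: "Reported advantages of this technique include the need for less material per incision, lower closure costs, shorter length of closure time". That passage reports earlier studies of barbed suture as a wound closure option. It does not place the suture in the deep layers, and nothing shows that deep technique varies among the participating surgeons.

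Finally, timing only the skin step could hide real cost if a device needs more or less work beneath it. This would be a fair objection if the skin step were the only time kept. The schedule already records operative times separately, so that cost remains visible.

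**Conclusion.** The point holds as one of precision and endpoint definition. Surgeon is not named in allocation or analysis, and closure time is undefined although the zipper closes only the most superficial layer. For closure time the loss may be material: an SE of 0.49 to 0.77 min instead of 0.35 min from whole-wound timing, and an SE that adjusting for surgeon would cut by 11% to 29%. Both ranges rest on the assumed SDs and variance shares, since the plan supplies none. For complications the effect of chance imbalance is small relative to sampling error.

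Two stronger readings are tempting. One is that the device effect is biased by background technique. That requires deep closure to differ by arm. Unblinded surgeons with advance knowledge of the arm make it possible, but the documents do not show it, and the risk comes from Sections 3.2, 3.4 and 4, not from the usual-practice sentence in Section 3.3. The other is that deep-layer noise would drown the skin-step difference. The plan gives no expected difference, so a loss of precision is as far as the evidence goes.

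**What to change.** 1. **Sections 3.2 and 5.2.** Replace the alternating method with concealed random allocation in blocks of varying size within surgeon, grouping low-volume surgeons. Include surgeon in the closure-time and cost models, and give a surgeon-stratified estimate for complications.
2. **Section 2.3 and the schedule in Section 4.** Define closure time as the skin step, from completion of the layer beneath to completion of the assigned closure. Keep the separately recorded total operative time for the cost objective in Section 1.4.
3. **CRF.** Record the surgeon and the deep-layer closure material. No technique needs to be prescribed; the record lets the analyst see whether deep closure differed by arm.

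The cost is a slightly more complex allocation list, one extra time stamp in theatre and one or two CRF items. The allocation list, the timing definition and the CRF items need to be in place before enrolment; the model terms need only be fixed before the data are analysed.
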